5 SAMPLE SIZE AND POWER

The primary efficacy endpoint is a composite endpoint comprising investigator and subject assessments of treatment effectiveness using the FWS. Composite endpoint treatment success (CETS) is defined as ≥ 2 point reduction in FWS score at maximum frown achieving a score of 0 or 1 at the visit week 4 relative to baseline based on investigator assessment and subject assessment. Thus, a subject is a CETS “Responder” only if both investigator- and subject-rated success criteria are satisfied at the visit 4 weeks after baseline.

The primary analysis of efficacy is the proportion of responders in the BoNT/A-DP treatment group compared with the placebo treatment group. For superiority testing of BoNT/A-DP compared with placebo, the following assumptions for the sample size calculation will be used:

Item	Assumption	Comments
Underlying test	Fisher's Exact Test	Standard test for a response parameter for small numbers
Randomization scheme (BoNT/A-DP: Placebo)	3:1	More active treatment subjects to enlarge safety database
Power $1-\beta$	90%	Actual power is 92.3%
Significance level (α)	0.025 one-sided	
Response Arm BoNT/A-DP	46%	Conservative value based on the results of previous studies (BLESS I and BLESS II)
Response Arm Placebo	2%	Conservative value based on the results of previous studies (BLESS I and BLESS II)
Software		The sample size calculation was performed using the software nQuery Advisor [®] 8.2.1.0

Statistical Analysis Plan (SAP)

CROMA
est. 1976

Based on these assumptions, 39 subjects in the BoNT/A-DP arm and 13 subjects in the placebo arm are required, i.e., 52 subjects in total. This is a very small sample size and not sufficient for a detailed evaluation of the data, including subgroup analyses. Furthermore, the response rate could not be estimated with sufficient precision. Assuming a response rate of 46% in the BoNT/A-DP group, a two-sided confidence interval (CI) of 95% with a distance from the response rate to the CI limits of about 5.6% could be achieved with a sample size of 225 subjects in the BoNT/A-DP group. A 3:1 randomization of BoNT/A-DP (225 subjects) to placebo (75 subjects) is proposed, which is adequate for a precise estimate of response rate and for post-hoc sensitivity analyses (i.e., treatment-by-center and other subgroup analyses), also taking into account a drop-out rate.

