- of subjects with an improvement of ≥ 2 points in FWS at maximum frown at 4 weeks after re-treatment,
- of subjects with ≥ 1 point reduction in FWS score at maximum frown (at weeks 1, 2, 4, 8, 12, 16 and 20 relative to baseline,
- of subjects with ≥ 1 point reduction in FWS score at maximum frown at week 4 relative to re-treatment baseline,

the CMH test (with stratification variable site) and the Pearson χ^2 -test will be applied. In case of a total number of observations below 30, or in case of at least one cell frequency below 5, Fisher's exact test will be used instead of the χ^2 -test. Two-sided 95% CIs for response rates will be calculated, where appropriate. Additionally, the cumulative proportions of effects at weeks 1, 2, and 4 will be calculated.

Time to onset of effect in the first treatment cycle will be analyzed descriptively and by using the Kaplan-Meier method. Moreover, the daily assessments of the line severity when frowning will be analyzed descriptively. The FACE-Q satisfaction with outcome scale will be analyzed descriptively.

All efficacy endpoints, with the exception of “responder” 4 weeks after re-treatment, will be analyzed for the first treatment cycle only. The analysis of “responder” 4 weeks after re-treatment will be conducted on observed values only, i.e., subjects with missing investigator or the subject in-clinic assessments on FWS week 4 or at the preceding end of the cycle visit will be excluded from analysis. Subjects who were treated with placebo during the first treatment cycle are excluded from the analysis of this endpoint, but not assigned as being non-responders. A two-sided McNemar test (using a significance level of 0.05) will be used to compare the response proportions between week 4 re-treatment visit and at the preceding end of the cycle visit. These endpoints will be separately analyzed for each open label extension cycle.

In addition to the FAS population, the analyses of these endpoints will also be based on the MFAS and PP populations. For all analyses, a one-sided significance level of 0.025 will be used, if not stated otherwise. Additional exploratory subgroup analyses will be conducted as described in Section 8.8.

Statistical Analysis Plan (SAP)

CROMA
est. 1976

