8.8 Other Analysis

8.8.1 Subgroups

The following subgroup analyses will be performed for the primary efficacy endpoint. Subgroup analyses a) and b) will also be conducted for the key secondary efficacy endpoint and for the additional secondary efficacy endpoints ‘the percentage of responders at week 12 (after the first treatment)’, the percentage of responders at week 16 (after the first treatment)’, ‘the percentage of responders at week 20 (after the first treatment)’ and ‘the proportion of subjects with a ≥ 1 point reduction in FWS score at rest at week 4 in the first treatment cycle, based separately on the investigators’ and the subjects’ in-clinic assessments (applicable only for subjects who have a FWS score at rest ≥ 1 at baseline)’:

a) Subgroup analysis by site and country.

Subgroup analyses will be conducted by site and country. Sites with less than three placebo subjects will be combined. The χ^2 -test will be applied for each subgroup. In case of a total number of observations below 30, or in case of at least one cell frequency below 5, Fisher’s exact test will be used instead of the χ^2 -test. Stratified analyses applying the CMH test will also be conducted using factor country. 95% CIs will be presented, if applicable.

b) Subgroup analysis by subjects with previous use of botulinum toxin versus naïve subjects.

Subgroup analyses will be conducted for subjects with treatment with any serotype of botulinum toxin for any indication versus naïve subjects. The χ^2 -test or Fisher’s exact test (see above corresponding criteria to use Fisher) will be applied for each subgroup. No stratified analysis using factor pre-treated/naïve subjects is currently planned. 95% CIs will be presented, if applicable.

Statistical Analysis Plan (SAP)

CROMA
est. 1976

c) Subgroup analysis by race (American Indian or Alaskan Native, Asian, Black or African American, Native Hawaiian or Other Pacific Islander, Caucasian (Including Hispanic or Latino and Other)). The χ^2 -test or Fisher's exact test (see above corresponding criteria to use Fisher) will be applied for each subgroup. No stratified analysis using factor race is currently planned. 95% CIs will be presented, if applicable.

d) Subgroup analysis of:

- subjects with previous use of botulinum toxin by site
- naïve subjects by site

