The χ^2 -test or Fisher's exact test (see above corresponding criteria to use Fisher) will be applied for each subgroup. No stratified analysis using site is currently planned. 95% CIs will be presented, if applicable.

e) Subgroup analysis by Fitzpatrick skin type (TYPE I, TYPE II, TYPE III, TYPE IV, TYPE V, and TYPE VI). The χ^2 -test or Fisher's exact test (see above corresponding criteria to use Fisher) will be applied for each subgroup. No stratified analysis using factor Fitzpatrick skin type is currently planned. 95% CIs will be presented, if applicable.

f) Subgroup analysis by sex. The χ^2 -test or Fisher's exact test (see above corresponding criteria to use Fisher) will be applied for each subgroup. No stratified analysis using factor sex is currently planned. 95% CIs will be presented, if applicable.

g) Subgroup analysis by ethnicity (Hispanic or Latino versus Not Hispanic or Not Latino). The χ^2 -test or Fisher's exact test (see above corresponding criteria to use Fisher) will be applied for each subgroup. No stratified analysis using factor ethnicity is currently planned. 95% CIs will be presented, if applicable.

h) Subgroup analysis by age groups (below 65 years, 65-74 years and 75-84 years). The χ^2 -test or Fisher's exact test (see above corresponding criteria to use Fisher) will be applied for each subgroup. No stratified analysis using factor age group is currently planned. 95% CIs will be presented, if applicable.

i) Subgroup analysis by additional age groups (below 65 years versus 65 years and older). The χ^2 -test or Fisher's exact test (see above corresponding criteria to use Fisher) will be applied for each subgroup. No stratified analysis using factor additional age group is currently planned. 95% CIs will be presented, if applicable.

Statistical Analysis Plan (SAP)

CROMA
est. 1976

Subgroups analyses will also be performed as follows for select additional secondary efficacy endpoints at select timepoints:

- The proportion of subjects with ≥ 1 point reduction in FWS score (at maximum frown) in the BoNT/A-DP and placebo groups during the first treatment cycle at week 4 relative to baseline, based on both the investigators' and the subjects' in-clinic assessments: all subgroups

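### Outside site, the SAP's subgroup analyses give within-subgroup tests but no comparison of effects between levels, and in the prior-use-by-site cells those tests are too weak to inform on consistency

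*SAP*

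**What the plan says.** SAP 8.8.1 lists subgroup analyses a to i for the primary endpoint: site and country, prior toxin use against naïve, race, prior use within site, Fitzpatrick type, sex, ethnicity and two age groupings. Each uses a chi-square test within the subgroup, replaced by Fisher's exact test when there are fewer than 30 observations or any cell count is below 5. Each item also promises 95% confidence intervals where applicable, without saying whether they are for the rate in each arm or for the difference. The only interval method named for the primary endpoint (SAP 8.6.2) is Wilson, for the rate in each arm.

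Item b, prior use overall, says "No stratified analysis using factor pre-treated/naïve subjects is currently planned". Item d takes "subjects with previous use of botulinum toxin by site", then naïve subjects by site, and says "No stratified analysis using site is currently planned". The remaining non-site items carry similar sentences. Country gets a stratified CMH test.

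The one planned test of whether effects differ is Breslow-Day by center (SAP 8.6.1.2). SAP 8.9 extends it to responders at weeks 12 and 16 and to the at-rest endpoint. SAP 8.6.1.1 makes everything outside the testing hierarchy exploratory.

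**The concern.** A subgroup analysis should show whether the effect differs between levels of a factor. A p-value computed inside one level mixes the size of the effect with the size of the cell. With 3:1 allocation the placebo side of a small cell holds only a handful of subjects, so a cell can miss significance while behaving exactly as the trial assumes.

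This matters because SAP section 5 rejects a 52-subject trial partly as too small for subgroup analyses, and names subgroup analyses again in support of the larger size. As planned, the small-cell output would be a scatter of significant and non-significant results that mostly reflects cell size. For the non-site factors there would be no estimate of how far the effects differ. What is at stake is the reading of exploratory tables, not the trial's main claim.

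**Working it through.** **Inputs from the documents.**
- Response rates: "Assuming a response rate of 46% in the BoNT/A-DP group" and 2% on placebo (SAP section 5).
- Level: "0.025 one-sided" in the sample-size table, and "For all analyses, a one-sided significance level of 0.025 will be used, if not stated otherwise" (SAP 8.6.4).
- Allocation 3:1, 353 subjects, about 7 sites (SAP 3.1, 3.2.1 and 5). 353/7 = 50.4 per site, in line with the 48 to 52 in the protocol synopsis, so a site is about 38:13 (active:placebo).

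**Assumptions not in the documents.** Equal site sizes, and a smaller prior-use stratum of 20% to 50% of subjects.

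**Which test applies.** At a 2% placebo rate, 13 placebo subjects yield 13 × 0.02 = 0.26 expected responders. The placebo-responder cell will be below 5 and Fisher's test will be used.

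**Formula.** Power = sum over all tables (x, y) with one-sided Fisher p ≤ 0.025 of Bin(x; n₁, 0.46) × Bin(y; n₂, 0.02).

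**The plan's own figure.** At 39:13 this gives 0.9227, matching the SAP's 92.3%. At 36:12 it gives 0.876, so 39:13 is the smallest 3:1 size above 90%.

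**Power by cell size.**

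| Cell (active:placebo) | Power |
|---|---|
| 38:13 (whole site) | 0.908 |
| 26:9 | 0.621 |
| 23:8 | 0.450 |
| 19:6 (half a site) | 0.186 |
| 15:5 | 0.081 |
| 12:4 | 0.038 |
| 6:2 | 0 |

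Two of these can be checked by hand.
- 6:2. The most extreme table is six active responders and no placebo responders: p = 1/C(8,2) = 1/28 = 0.036. This exceeds 0.025, so the cell cannot be significant.
- 19:6 with no placebo responders. Ten active responders give p = C(19,10)/C(25,10) = 92,378/3,268,760 = 0.028. Eleven give C(19,11)/C(25,11) = 75,582/4,457,400 = 0.017. So 11/19 = 58% must respond, against the 46% assumed.

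**Prior use by site: 7 × 2 = 14 cells.** With every cell fixed at 19:6, the expected number significant is 14 × 0.186 = 2.6. Real cells would vary in size. A 4,000-run simulation with the same 46% versus 2% effect in every cell and a binomial prior-use split at each site gives:

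| Prior-use split | Expected significant of 14 | Trials with more than half non-significant |
|---|---|---|
| 50:50 | 3.7 | 97% |
| 40:60 | 3.9 | 96% |
| 30:70 | 4.5 | 94% |
| 20:80 | 5.2 | 87% |

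**Sensitivity.** With the BLESS II rates (48.8% and 1.9%) the expected number is 4.6 to 5.7 of 14, and with the BLESS I rates (46.5% and 0%) 4.3 to 5.9. Six sites give 4.9 to 5.3 of 12 and eight sites 2.9 to 4.9 of 16. Five sites give 4.9 to 5.9 of 10, so a majority of cells would no longer be non-significant.

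**Prior use overall (item b).** A stratum with 25% of subjects (66:22) has 99.8% power, and one with 20% (53:18) has 98.7%.

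**What a direct comparison would give.** In the same simulation, a test of the difference between the two strata's risk differences, pooled over sites, signals falsely in about 3% to 4% of trials at the two-sided 5% level. The 95% half-width for that contrast is about 14 points at a 50:50 split and 18 points at 20:80.

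**The case against.** The strongest reply is that neither document says consistency will be judged by these p-values. That is correct. A reader might infer it from the list of within-subgroup tests, but SAP 8.8.1 gives no decision rule and SAP 8.6.1.1 labels the analyses exploratory. The supportable statement is narrower: outside site, nothing else is planned that would address consistency.

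A reader might also infer that site consistency is left to separate tests. It is not, because Breslow-Day is planned and sites with fewer than three placebo subjects are combined. Nor does the sentence in item b show a power problem, since the overall prior-use strata are large. A stratified CMH analysis there would in any case give an adjusted common effect, not a test of whether effects differ.

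Confidence intervals are promised, and the table templates sit in a separate document. The intervals may turn out to be for differences, but the SAP text does not commit to that.

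The counts also depend on a pre-treated share that the documents do not give, and on planning rates that the SAP calls conservative. Both are fair points. The count stays a minority of cells at six to eight sites under the 46% and 2% rates, and at seven sites under either earlier trial's rates. What stands is the missing comparison of effects for the non-site factors and the uninformative tests in the small cells.

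**Conclusion.** The point holds as a minor improvement to exploratory output. For prior use, race, skin type, sex, ethnicity and age, the SAP plans within-level tests and unspecified intervals, with no estimate or test of a difference in effect. In item d, and in any race or skin-type category of similar size, the tests say little: power is about 19% at 19:6, 4% at 12:4 and nil at 6:2. With about seven sites and the same effect everywhere, roughly 3 to 5 of 14 prior-use-by-site cells would reach significance.

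This rests on the 46% and 2% rates, one-sided 0.025, equal sites and a smaller prior-use stratum of 20% to 50%. The primary and key secondary conclusions are unaffected.

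**What to change.** In SAP 8.8.1:

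1. For each subgroup level, report the between-arm difference in responder rate with a 95% confidence interval by a named method, for example Newcombe, in place of the within-subgroup p-value.
2. For each non-site factor, add one treatment-by-factor heterogeneity test on the risk-difference scale. For a two-level factor, give the difference between the two risk differences with its interval. State that power is low; the half-widths of 14 to 18 points for prior use show the limit. Avoid the odds-ratio scale for these factors, because empty placebo cells are likely: with 13 placebo subjects the chance of no responder is 0.98^13 = 77%, and with about 88 it is still 0.98^88 = 17%. State how zero counts enter the variance.
3. Show the prior-use-by-site cells (item d) descriptively, with counts and rates and no p-values.

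The cost is SAP wording and re-specified exploratory tables, with fewer p-values and no new data. SAP 8.9 places the primary-endpoint subgroup analyses in the interim analysis and does not repeat them, so the change belongs before that unblinding.

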This benefit was maintained up to Week 16 post-injection for approximately 20% of subjects. Composite rates of ≥ 1 point improvement in FWS at maximum frown were 45.1% and 1.2%, respectively, in the BoNT/A-DP and placebo groups, at Week 12, 20.8% and 0.6%, respectively, at Week 16, and 9.9% and 0.0%, respectively, at Week 20 (p < 0.001 in each instance).

Consistent with the primary endpoint, efficacy was maintained with up to 3 retreatments, with 81.5%, 74.4% and 70.3% of subjects in the BoNT/A-DP group at Week 4 after the first, second and third retreatment cycles, respectively, having shown composite rates of ≥ 1 point improvement in FWS at maximum frown (with rates of 93.1%, 91.1% and 87.4% of subjects as assessed by investigators; and 84.4%, 76.7% and 73.4% of subjects, as assessed by subjects after the first, second and third retreatment cycles, respectively).

No deaths and no study drug-related SAEs were reported during the study. One (0.1%) subject during the study reported a BoNT/A-DP-related AE that led to discontinuation (headache; during the open-label phase). Pregnancy led to discontinuation from the study for 3 subjects.

During the double-blind phase of the study, 19 (3.6%) subjects experienced TEAEs considered to be at least possibly related to BoNT/A-DP and 4 (2.3%) subjects experienced TEAEs considered to be at least possibly related to placebo. Study drug-related TEAEs in the BoNT/A-DP and placebo groups, respectively included headache: 10 (1.9%) subjects and 1 (0.6%) subject; injection site pain: 2 (0.4%) subjects and 1 (0.6%) subject; and head discomfort: 2 (0.4%) subjects in the BoNT/A-DP group and none in the placebo group. The rate of headache was higher in the BoNT/A-DP group compared to the placebo group. All other events were experienced by no more than 1 (0.1%) subject.

One AESI was reported for 1 (0.1%) subject each in the BoNT/A DP and placebo groups during the double-blind phase and 3 (0.4%) subjects in the open-label phase. A total of 3 (0.4%) subjects had AESIs related to BoNT/A-DP and 2 (0.3%) subjects had AESIs related to injection procedure. No subjects had AESIs related to placebo or injection procedure.

A secondary objective of the study was to provide long term safety data of BoNT/A-DP based on multiple treatment cycles. This study showed no increases in TEAE rates or TEAE severity with up to 4 cycles of treatment, thus confirming safety after repeated treatments and over prolonged period of use.

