11. The percentage of subjects with a FWS score of 0 or 1 and an improvement of ≥ 2 points in FWS score at maximum frown (investigator and subject assessment) at four weeks after re-treatment relative to the rating at the preceding end of cycle visit.
12. The proportion of subjects with ≥ 1 point reduction in FWS score (at maximum frown) in the BoNT/A-DP and placebo groups during the first treatment cycle at weeks 1, 2, 4, 8, 12, 16 and 20 relative to baseline, based on both the investigators' and the subjects' in-clinic assessments.
13. The proportion of subjects with ≥ 1 point reduction in FWS score (at maximum frown) in the BoNT/A-DP group during each re-treatment cycle at week 4 relative to re-treatment-baseline, based on both the investigators' and the subjects' in-clinic assessments.

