- The proportion of subjects with ≥ 1 point reduction in FWS score (at maximum frown) in the BoNT/A-DP and placebo groups during the first treatment cycle at week 12, 16 and 20 relative to baseline, based on both the investigators' and the subjects' in-clinic assessments: by site, by country and by subjects with previous use of botulinum toxin versus naïve subjects.

Subgroup analyses will be performed on the FAS, MFAS and PP populations.

COVID-19 Pandemic:

Due to COVID-19 pandemic, the secondary endpoints 'the percentage of subjects with an improvement of ≥ 2 points in FWS at maximum frown at 4 weeks after re-treatment' and 'the percentage of subjects with ≥ 1 point reduction in FWS score at maximum frown at week 4 relative to re-treatment baseline' will be also analyzed using observed values by the FWS investigator assessment type (i.e. assessment done remotely or physically). The objective is to assess if the remote way has not impacted the investigator assessment.

These analyses will be performed for the final analysis.

Exclusion of Site 110 Subjects:

A site audit conducted in January 2019 as pointed out a critical finding on a protocol non-compliance: an unblinded site staff performed blinded tasks on safety assessments. In order to assess the impact on the results, analyses based on FAS for primary and secondary efficacy endpoints relative to the double-blind period of the trial will be repeated excluding all the subjects of the site 110.

AE summary tables for TEAEs and AESIs, and TEAEs and AESIs summarized by SOC, PT will be also repeated for each site and by excluding all the subjects of the site 110.

These analyses will be performed for the interim and final analyses.

Statistical Analysis Plan (SAP)

CROMA
est. 1976

ADA, laboratory, vital signs and ECG analyses will be also repeated by excluding all the subjects of the site 110 only for the final analysis.

Further analyses may be performed to assess the site 110 effect, if needed.

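### The SAP's check on remote investigator ratings uses composite investigator-and-subject endpoints, which barely respond to upward investigator drift, and gives no interval for the remote-minus-physical difference

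*SAP*

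**What the plan says.** SAP 3.3 records that visits could be held remotely while a site was closed because of the pandemic. In the COVID-19 part of SAP 8.8.1, two re-treatment endpoints "will be also analyzed using observed values by the FWS investigator assessment type", that is, remote or physical. The purpose is stated as: "The objective is to assess if the remote way has not impacted the investigator assessment".

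Both endpoints need two raters. Endpoint 11 in SAP 4.3 is a score of 0 or 1 with at least a 2-point improvement, measured on this basis: "FWS score at maximum frown (investigator and subject assessment) at four weeks after re-treatment relative to the rating at the preceding end of cycle visit". Endpoint 13 is a reduction of at least 1 point "relative to re-treatment-baseline, based on both the investigators' and the subjects' in-clinic assessments".

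SAP 8.6.4 plans two-sided 95% CIs for response rates where appropriate, and SAP 8.1 has a similar general convention. The McNemar test in both sections compares week 4 after re-treatment with the preceding end-of-cycle visit. It does not compare remote with physical. Section 8.8.1 sets no test, margin or decision rule for that comparison.

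**The concern.** The question is about one rater, but the yardstick requires two raters to agree. A subject counts only if investigator and subject both score a response, and earlier data show that the subject is usually the stricter of the two. If remote viewing led investigators to rate lines as milder, most of the extra investigator-rated responses would fall in subjects who do not rate themselves responders, and the composite would hardly move.

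The stated aim is also to establish an absence of effect. Two similar rates do not establish that without an interval for their difference. At stake is whether the final report can say anything reliable about remote investigator ratings in the repeat-treatment results. The documents give no evidence on which way remote viewing would shift ratings, so both directions need to be visible.

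**Working it through.** The check states no sample size, power or margin, so there is no figure of the plan's to reproduce.

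**Inputs.** Week-4 active-treatment rates from Protocol 4.4.2.1 (BLESS I) and 4.4.2.2 (BLESS II). For the ≥1-point re-treatment measure, BLESS I reports the composite and subject rates below, "with rates of 93.1%, 91.1% and 87.4% of subjects as assessed by investigators". The strict measure (0 or 1 with ≥2 points) is reported by rater only for cycle 1, so those rates stand in for re-treatment.

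**Ceiling on upward drift.** If remote investigators score everyone a responder and subject scoring is unchanged, the composite equals the subject rate. Its maximum rise is subject minus composite. The investigator rate rises by 100 minus its current value.

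| Measure | Composite % | Subject % | Investigator % | Max composite rise | Investigator rise |
|---|---|---|---|---|---|
| ≥1 point, re-treatment 1 | 81.5 | 84.4 | 93.1 | 2.9 | 6.9 |
| ≥1 point, re-treatment 2 | 74.4 | 76.7 | 91.1 | 2.3 | 8.9 |
| ≥1 point, re-treatment 3 | 70.3 | 73.4 | 87.4 | 3.1 | 12.6 |
| Strict, BLESS I cycle 1 | 46.5 | 55.6 | 66.5 | 9.1 | 33.5 |
| Strict, BLESS II cycle 1 | 48.8 | 51.9 | 75.0 | 3.1 | 25.0 |

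**Chance of missing that extreme.** The remote count is not in the documents; I assume 20, 40 or 80 remote against 200 physical ratings per cycle. The test is a pooled two-proportion z-test, two-sided 5%, by exact enumeration. It is my illustration, since the SAP specifies none.

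- ≥1-point composite: missed 92-96% of the time.
- Strict composite: missed 72-87% at BLESS I rates and 92-94% at BLESS II rates.
- Strict response by the investigator alone: missed about 0% of the time.

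The 80-remote case is an upper bound. SAP 8.6.4 excludes first-cycle placebo subjects from the re-treatment responder analysis, and 353 × 3/4 is about 265 active subjects before dropout, fewer than 80 + 200 = 280.

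**Moderate downward drift.** Suppose the remote investigator ≥1-point rate falls by 15 points and the composite falls in proportion: fall = composite × 15 / investigator rate. For re-treatments 1 to 3 this gives 81.5 × 15/93.1 = 13.1, 74.4 × 15/91.1 = 12.3 and 70.3 × 15/87.4 = 12.1 points. The composite comparison misses this 34-78% of the time; the investigator's own rate misses it 7-54%.

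**Gross downward drift.** If remote investigators scored nobody a responder, the composite would be 0%. That is detected with near-certainty even with 10 remote against 200 physical ratings.

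**Precision.** The 95% half-width for a difference is 1.96 × √[p₁(1−p₁)/n₁ + p₂(1−p₂)/n₂]. For re-treatment 3 at the ceiling (73.4% of 20 against 70.3% of 200) it is 20.4 points. Across five assumed splits, from 20:200 to 150:150, and all the measures, it runs from about 8.5 to 23 points.

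**Effect on the endpoints themselves.** The shift in a pooled rate is maximum rise × remote / (remote + 200). For ≥1 point it runs from 2.3 × 20/220 = 0.2 to 3.1 × 80/280 = 0.9 points. For strict BLESS I it runs from 9.1 × 20/220 = 0.8 to 9.1 × 80/280 = 2.6 points.

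**The case against.** Several points on the other side stand.

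- A reader might infer that the plan gives no intervals at all. It does plan 95% CIs for individual rates. What is missing is one for the remote-minus-physical difference.
- A reader might infer that the check would report no impact whatever happened. The documents do not support that: no rule exists to produce such a report, a conventional test would sometimes detect the extreme upward case (4-35% over the five splits), and a gross fall would be obvious.
- A reader might infer that remote ratings will be pooled on the strength of this check. Section 8.8.1 makes no pooling decision depend on it, and splitting by type already yields a physical-only result. SAP 7.2.1 excludes subjects with missing in-clinic ratings from the re-treatment responder analysis, so whether remote ratings enter endpoint 11 at all is unsettled. In SAP 4.3 only endpoint 13 specifies in-clinic ratings.
- The subject-rating cap that hides upward drift also shields the endpoints from it, as the last calculation shows.
- The endpoints are open-label and outside the confirmatory hierarchy; SAP 8.6.1.1 makes them exploratory.

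The short labels in 8.8.1 omit the rater, so investigator-only rates may have been meant, and the table shells are in a separate document. But 8.8.1 calls them secondary endpoints, and 4.3 defines those on both raters. If investigator-only was intended, the text should say so.

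These points limit the harm. They do not make a two-rater composite a measure of one rater.

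**Conclusion.** The point holds as a minor one. The planned comparison cannot isolate the investigator's rating: upward drift would probably go unseen, moderate downward drift is diluted, and only gross downward drift would clearly show. Without an interval for the difference, similar rates cannot support a statement that remote working had no effect.

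The ceilings come from figures in the Protocol and assume unchanged subject scoring. The miss rates also rest on assumed remote counts, an illustrative test, prior-study rates carrying over and, for the strict measure, cycle-1 rates standing in for re-treatment rates. Bias in the pooled ≥1-point rate would be under about 1 point even in the extreme upward case. The primary and key secondary results come from cycle 1 week 4 and are not affected.

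**What to change.** In SAP 8.8.1, keep the planned tables and add the following at the week-4 re-treatment visit, by assessment type, each with the remote-minus-physical difference and its 95% CI:

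1. Investigator-only response rates, for ≥1 point and for a score of 0 or 1 with ≥2 points.
2. As a supportive measure, the investigator-minus-subject FWS score difference at maximum frown. Note that the subject's rating may itself have been made away from the clinic, so it is an imperfect reference.

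The second item is useful because the investigator-only ≥1-point rate has its own ceiling. With 20 remote ratings it would miss the everyone-a-responder case 94-100% of the time, and its power reaches 86% or more only with 75 or more remote ratings.

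State that similar, or not significantly different, composite rates will not be read as no impact, and that a wide interval will be reported as inconclusive. If the sponsor wants to conclude no impact, it should set and justify a margin before the final analysis; the documents offer no basis for a particular value.

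The cost is a few lines of SAP text and one or two extra tables. Investigator and subject scores are both recorded in the CRF, and assessment type is already the grouping variable. The downside is that, with few remote ratings, the answer may be inconclusive.
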